6.1 Administration Protocol

VIDITUOM: 2.0mg/kg, iv drip, q3w every 21 days for 4 cycles;

Ampley monoclonal antibody: 200mg, iv drip, q3w, in a cycle of 4 cycles every 21 days.

Order of use: Vidicidone monoclonal antibody → PyAmpley monoclonal antibody.

Radical cystectomy was performed 4 weeks after the neoadjuvant treatment.

6.2 Combined treatment (permitted adjuvant, supplemental/alternative therapies)

All concomitant medications during the study (generic name of the drug, purpose of administration, dose administered, time of administration, etc.) must be detailed on the case report form. Other clinical trial drugs were prohibited during the study.

Combination therapies are prohibited as follows:

1) Similar anti-HER2 therapeutic drugs.

Drug-drug interaction studies with this product have not been formally conducted in patients. To characterize the potential drug-drug interaction of the free MMAEs, results from another drug-drug interaction study with an ADC drug coupled with the same cytotoxic monomethyl-Australian statin E(MMAE) are presented below:

2) the effect of other drugs on vidicon for injection:

CYP3A4 potent inhibitors: Other MMAE-coupled ADC drugs in combination with ketoconazole, a potent inhibitor of CYP3A4, will increase the exposure of free MMAEs by 25% in Cmax and 34% in AUC; There is no effect on the ADC exposure. It is hypothesized that coadministration of this product with a potent inhibitor of CYP3A4 will have the same effect on exposure to free MMAE and bound antibodies as the ADC drug.

CYP3A4 potent inducers: Other MMAE-coupled ADC drugs in combination with rifampin, a potent inducer of CYP3A4, reduced exposure of free MMAEs by 44% in Cmax and 46% in AUC; There is no effect on the ADC exposure. It is hypothesized that coadministration of this product with a potent inducer of CYP3A4 will have the same effect on exposure to free MMAE and bound antibodies as the ADC drug.

Other drug effects of vidicon mab for injection: CYP3A4 substrates: Other MMAE-coupled ADC drugs in combination with midazolam, a sensitive CYP3A4 substrate, did not affect midazolam exposure. It is also hypothesized that this product will not affect exposures of drugs metabolized by CYP3A4 enzymes.

VII. Study intervention discontinuation/subject discontinuation and withdrawal *

7.1 Test Termination/Suspension Criteria

The sponsor has the right to terminate/suspend this test. The Sponsor must notify the investigator, the Ethics Committee, and the State Food and Drug Administration with reasons prior to terminating/suspending a clinical trial. Resumption of the study following early termination/suspension of the study must be approved by the Ethics Committee review;

Termination/suspension requested by the ethics committee.

7.2 Provisions for Conclusion of Clinical Trials

The trial ended when all subjects:

1) All subjects complete a survival follow-up of at least 2 years;

2) or all subjects died, were lost to follow-up, or withdrew their informed consent.

VIII. Adverse events and unexpected events

8.1 Adverse Events

8.1.1 Definition of adverse event

An adverse event is any adverse medical event that occurs after the patient or subject has received a medication and is not necessarily causally related to treatment. Thus, an adverse event could be any adverse sign (including abnormal laboratory results), symptom, or disease temporally related to the use of study drug, regardless of whether a causal relationship with study drug was considered.

8.1.2 Classification of adverse events

Adverse events included Serious Adverse Event, SAE) and non-serious adverse events.

8.1.3 serious adverse events

SAE refers to the medical events that need hospitalization or prolong hospitalization, cause disability, affect the ability to work, endanger life or death, and lead to congenital malformations in the process of clinical trials. Include the following medical events:

- 1) an event leading to death;
- 2) A life-threatening event (defined as a condition in which the subject was in immediate danger of death at the time of the event);
- 3) Events requiring hospitalization or prolonging hospitalization;
- 4) Events that can lead to permanent or severe disability/dysfunction/impact on work ability;
- 5) Congenital abnormality or birth defect;

Other important medical events (defined as events that endangered the subject or required intervention to prevent any of the above).

If the SAE of death occurs as a result of disease progression (at the discretion of the investigator), the SAE may be considered for non-escalation and dealt with in accordance with the medical practice at each center.

8.1.3 Evaluation of adverse events

(Severity of adverse event, relationship between adverse event and study, whether adverse event is known as adverse event of study intervention, etc.)

Severity will be assessed based on five criteria established by the NCI CT Cae Version 5.0:

Level 1, mild; No symptoms or slight signs; It is only for clinical or diagnostic observation and does not need medical intervention;

Level 2, moderate; • Age-appropriate limitations on activities of daily living (activities of daily living such as cooking, shopping, and making phone calls);

Grade 3, serious or medically important but not immediately life-threatening; Resulting in

hospitalization or prolonged hospitalization; Disability; Limited activities of daily living (activities of daily living refer to bathing, dressing, undressing, eating, going to the toilet, and taking medicine, but they are not bed-ridden);

Level 4, life threatening, requiring emergency treatment;

Level 5, AE-related death

8.1.4 Reporting of adverse events

Collection, reporting and handling of aes in 8.1.4.1

All AEs related to the protocol-specified procedures that occurred after the informed consent form was signed and prior to administration of the test article were recorded on the CRF.

Records of AEs should include a description of the AE and all associated symptoms, when it occurred, severity, duration, association with test article, action taken, and final outcome and outcome. The recording of AEs must use medical terminology, and if subject symptoms and signs can be summarized by a common etiology, the diagnosis should be recorded as much as possible. In addition to the indicators related to disease progression, all clinical events and clinically significant laboratory adverse reactions could be handled with reference to the Evaluation Standard for Common Adverse Reaction Events (CT cae) version 5.0; Post-surgical AEs were only evaluated by Clavien-Dindo classification. Treatment-emergent adverse reactions will be documented by the investigator.

Collection and reporting of SAEs in 8.1.4.2

All SAEs, regardless of cause or drug-related, that occurred between the time the subject signed the informed consent form and 4 weeks after completion of study dosing were reported using the SAE Reporting Form. In the event of SAE, the investigator shall immediately take appropriate treatment measures for the subject to ensure the safety of the subject, and report to the drug registration applicant, National Medical Products Administration, the Provincial Food and Drug Administration, the ethics committees of the corresponding clinical trial centers, and the Medical Department of Health and Sanitation Committee, Medical Administration and Hospital Authority within 24 hours and to the ethics committee of the team leader unit in a timely manner. The initial report should, to the extent possible, include the following: source of report, test article name, serious adverse events name, time of occurrence, severity, duration, relevance to the test article, action taken, and outcome.

IX. Data collection and management

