5.2.5 Post-operative Follow-up/End of Surgical Treatment Visit (EOT)

These include one follow-up at week 1, one month, three months (EOT), six months, nine months, 12 months, 15 months, 18 months, 21 months, and 24 months after radical surgery, whichever occurs first, until the patient develops disease progression, dies, withdraws informed consent, loses follow-up, concludes the study follow-up, or begins new anticancer therapy (surgery).

End-of-surgical visit (EOT) was performed 90 days postoperatively (-14 to+28 days).

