		Determination of thyroid stimulating hormone TSH	

Abbreviations: CK-MB, creatine kinase cardiac isoenzyme; I. If considered regional standard treatment, test for this. II. If CK-MB portion is not available, evaluate troponin I and/or troponin T instead.

5.3.3.5 electrocardiogram

For safety monitoring purposes, the investigator must review all 12-lead ECG records, and sign and date them. Paper or electronic copies of the ECG will be maintained at the study center as part of the patient's permanent study file.

5.3.3.6 echocardiography: echocardiography is optional.

5.3.3.7 pulmonary function: pulmonary function tests are optional and the tolerance to radical surgery is evaluated.

Adverse events in 5.3.3.8

Drug and radical surgical AEs will be graded and documented throughout the study according to the NCI-CTCAE, Version 5.0, and Clavien-Dindo scoring system. Toxicity will be characterized by severity, duration, and time to occurrence.

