5.3.5 Visit window

All visits during neoadjuvant therapy were to be within the range of -3 to +7 days of the planned date, and postoperative visits were considered to be 14 days, unless otherwise noted. Evaluations scheduled for the day of study treatment dosing (Day 1) per cycle should be completed prior to study treatment infusion/dosing, unless otherwise noted. Laboratory and imaging results should be reviewed prior to dosing. Scheduling a study visit at a protocol-specified time point that is in conflict with a holiday, weekend, or other event/law will allow the visit to be scheduled to the nearest feasible date.

Visit schedule

	sift	Treatment period (one cycle every 21 days)				Drug safety follow-up r	operation		Postoperative follow-up				
		Cycle 1	Cycle 2	Cycle 3	Cycle 4		Preoperative evaluation	Radical resection	1 week	1 month	3 months (EOT)	6, 12, 18, 24 months	9, 15, 21 months
fate (window)	-28 to -1	one	-3 to +7	-3 to +7	-3 to +7	28 after last dose (-3 to +7)	-7 to 0	28 – 42 after the last dose	±3	±7	±14	±14	±14
Informed consent a	X												
Demographic data/ Treatment historyb	X												
Physical examination/vital signs c	X	X	X	X	X	X	X		X	X	X	X	
ECOG assessment	X	X	X	X	X	X	X		X	X	X	X	
Surgical fitness evaluation	X						X						
Electrocardiogram d	X	X	X	X	X	X	X		X	X	X		
Hematology e	X	X	X	X	X	X	X		X	X	X	X	
Serum biochemistry e	X	X	X	X	X	X	X		X	X	X	X	
Urinalysis e	X	X	X	X	X	X	X		X	X	X	X	
Fecal analysise	X			X			X						

Coagulation e	X						X						
Pregnancy testf	X					X	X						
Hepatitis b two half qualitative g	X						X						
Hepatitis c qualitative g	X						X						
Venereal disease (HIV)g	X						X						
Marker screening (HER2 IHC)	X												
Thyroid functionh	X						X						
Chest CT plain scan i	X			X		X	X				X	X	
Total abdominal+pelvic CT plain scan+enhanced i	X			X		X	X				X	X	
Bladder (or pelvis) Multiparameter mri	X			X			X						
Bone scan i	X												
Previous/concomitant medications	X	X	X	X	X	X	X	X	X	X			
Adverse eventj	X	X	X	X	X	X	X	X	X	X	X		
Vidicon monoclonal antibody administration k		X	X	X	X								
Ampley monoclonal antibody administration l		X	X	X	X								
Radical resection and pathological evaluation m								X					
Archived/fresh tumor histon	X							X					
EQ-5D-5L/ EORTC QLQ-C30 o	X	X	X	X	X	X	X	X	X	X	X	X	
Living condition	X	X	X	X	X	X	X	X	X	X	X	X	X

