J. AEs and laboratory abnormalities will be graded according to NCI-CT Cae Version 5.0 (drugs), and CLAVIEN-DINDO (surgery), and all AEs will be evaluated for severity. Only SAEs should be reported after informed consent has been signed but prior to initiation of study drug administration. After initiation of study drug, all AEs and SAEs, regardless of relationship of study drug and procedure, will be evaluated and documented until 28 days after the last dose (including chemotherapy) or initiation of new anticancer therapy (whichever occurs first). Assessment and documentation of surgery-related adverse events should be performed within 90 days after surgery.

K. VDT will be administered intravenously every 3 weeks. The infusion time for the first infusion (Cycle 1, Day 1) should be not less than 60 minutes; If well tolerated, subsequent infusions should take no less than 30 minutes, the shortest time allowed for an infusion. Patients must be monitored for at least 60 minutes in an area equipped with resuscitation equipment and emergency medications following the infusion of vidicon on the first day of Cycles 1 and 2. Beginning with cycle 3, a minimum of 30 minutes of monitoring is required in areas equipped with resuscitation equipment and emergency medications. VID should not be coadministered with any other drugs. At each cycle, vidicon will be administered prior to PD-1 drug administration.

L. PyAmpley monoclonal antibody will be administered intravenously every 3 weeks. Administration of the drug was on the same day as that of the vidicon.

M. After radical surgery, the pathological staging after neoadjuvant therapy will be evaluated by the investigator based on the pathological results of surgical samples.

N. During the screening stage, patients must provide tumor tissue samples of TURBT and relevant pathological report at the same time, and can choose to send fresh surgical tissue or pathological white sheet for biomarker analysis. Fresh tumor samples also need to be collected during radical surgery. Patients with disease progression will be asked if an optional biopsy has been performed (see central laboratory sample management manual).

O. Patients were required to complete the EQ-5D-5L and EORTC QLQ-C30 questionnaires (Appendix 11, 12). Where feasible, patients are required to complete questionnaires prior to administration of study drug or any other procedure.

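### The SAE form and footnote J's all-cause AE documentation both close by day 28 after the last dose, at or before the scheduled cystectomy, and other sections set different AE periods

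*Protocol*

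**What the plan says.** Five places in the protocol bear on how long events are collected.

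- **8.1.4.2 (SAE reporting).** SAEs of any cause that "occurred between the time the subject signed the informed consent form and 4 weeks after completion of study dosing were reported" on the SAE Reporting Form. A following sentence requires a report to authorities and ethics committees within 24 hours and names no period of its own.
- **Visit schedule, footnote J.** Once study drug has started, AEs and SAEs of any cause "will be evaluated and documented until 28 days after the last dose (including chemotherapy) or initiation of new anticancer therapy (whichever occurs first". It then adds: "Assessment and documentation of surgery-related adverse events should be performed within 90 days after surgery".
- **5.3.3.8 (adverse events).** "Drug and radical surgical AEs will be graded and documented throughout the study".
- **5.3.3.2 (physical examination).** Clinically important findings at follow-up visits that are new or have worsened go into the eCRF as AEs. There is no attribution test and no end date.
- **Visit schedule, adverse event row.** It is marked at 11 visits, including the preoperative evaluation, surgery, and 1 week, 1 month and 3 months after surgery. Footnote J qualifies this row.

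Surgery is placed at "28 – 42 after the last dose" (days) in the visit schedule. Section 6.1 says: "Radical cystectomy was performed 4 weeks after the neoadjuvant treatment". The SAE definition in 8.1.3 carries no 4-week limit and includes death and "Events requiring hospitalization or prolonging hospitalization".

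**The concern.** The two stated cut-offs fall no later than the earliest scheduled surgery date, yet the effect of the neoadjuvant therapy on cystectomy is part of a secondary objective (III.1.2 D). The form that documents SAEs is therefore not required for the period in which surgical SAEs would arise. Footnote J's wider net, which catches events whatever their cause, has also closed by then.

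The second problem is that the protocol gives sites different instructions. A site that follows footnote J stops recording non-surgical events at day 28. A site that follows 5.3.3.8 or 5.3.3.2 keeps recording them. The programme summary lists five centres, so counts of late drug-related and other non-surgical events could differ by centre for reasons unrelated to the patients. No analysis can recover events that a site was not told to record. The incidence or severity of AEs is also a ground for early termination (5.2.6), and safety is to be reviewed when 18 subjects are enrolled (5.4.1).

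**Working it through.** The plan gives no figure to reproduce. The check is a day count, with day 0 the last dose.

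**Inputs**
- The SAE form closes at 4 weeks: 4 × 7 = day 28 (8.1.4.2). Completion of dosing is taken to be the day of the last dose.
- All-cause documentation closes on day 28, or earlier if new anticancer therapy starts (footnote J).
- Surgery takes place on day S, with S from 28 to 42 (visit schedule). The 4 weeks in 6.1 give S = 28.
- The surgery-related AE window is 90 days after surgery (footnote J).

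**Formulas**
- Postoperative days 1 to 90 are days S + 1 to S + 90.
- Postoperative days inside a window closing on day 28: max(0, 28 − S).
- Days from the day-28 closure to the end of the 90-day window: (S + 90) − 28.
- Part of that span before surgery: S − 28.

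| Surgery day S | Postoperative days 1–90 | Days inside the day-28 windows | Day 28 to end of 90-day window | Of which before surgery |
|---|---|---|---|---|
| 28 | days 29–118 | 0 of 90 | 118 − 28 = 90 | 0 |
| 42 | days 43–132 | 0 of 90 | 132 − 28 = 104 | 14 |

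For every scheduled surgery date the overlap is zero. If surgery falls on day 28, the day of surgery itself is the last day covered.

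**Sensitivity.** If surgery were done off schedule on day 21 (an assumption), 28 − 21 = 7 postoperative days would fall inside the SAE-form window. Footnote J's window might still be shut, because 5.2.3 words surgery as a new anticancer therapy and footnote J closes when such therapy starts.

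**Instructions side by side, for an event after day 28 not judged surgery-related**
- Footnote J: no documentation required.
- 5.3.3.8: documented if it is a drug AE.
- 5.3.3.2: recorded if it is a clinically important new or worse finding at a follow-up visit. The schedule marks physical examination at 1 week and at 1, 3, 6, 12, 18 and 24 months after surgery.
- Adverse event row: marked up to 3 months, but subject to footnote J.

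**Two related windows also disagree**
- EOT visit: "End-of-surgical visit (EOT) was performed 90 days postoperatively" with −14 to +28 days in 5.2.5, that is 90 − 14 = 76 to 90 + 28 = 118 days after surgery. The visit schedule gives ±14 days; applied to 90 days, that is 76 to 104.
- Drug safety visit: −7 to +21 days in 5.2.3, that is days 21 to 49. The visit schedule and footnote Q give −3 to +7 days, that is days 25 to 35.

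**The case against.** The best reply is that little is actually lost. Footnote J keeps surgery-related AEs for 90 days. The secondary indicator uses CTCAE and Clavien-Dindo grading, not the SAE form. Clavien-Dindo grade 5 covers surgical deaths, and every death enters overall survival. Neither the interim safety review nor the termination ground is said to rely on the SAE form. Section 8.1.4.1 also has the investigator document treatment-emergent reactions without a time limit. All of this stands, and it confines the point to SAE reporting and to inconsistent AE periods.

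A reader might infer that any AE after day 28 is recorded only if the investigator attributes it to surgery, so that the protocol has a collection gap of 90 to 104 days. The documents do not support that. It is true of footnote J read alone, but 5.3.3.2 and 5.3.3.8 require more, and AEs are marked at five visits from the preoperative evaluation to 3 months. A reader might also infer that 24-hour reporting stops before surgery. The sentence states no period, so its reach is unclear, not excluded.

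The reply does not remove the core. The form's end date is explicit and falls no later than surgery, and the sections on AE collection cannot all be followed at once.

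**Conclusion.** The point holds in a limited form. All 90 postoperative days lie outside both the SAE-form window and footnote J's all-cause window for any surgery on days 28 to 42. As 8.1.4.2 is written, a postoperative SAE, including a death, needs no SAE form. Footnote J contradicts 5.3.3.8 and 5.3.3.2 and narrows the adverse event marks in the schedule. Non-surgical and late drug-related events can therefore be counted differently between sites, which weakens the secondary objective on safety and effect on cystectomy.

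This does not mean that postoperative complications go uncollected, and the primary endpoint is not affected. The protocol should be amended, but the fault is one of reporting periods and consistency. The conclusion assumes surgery on the scheduled days and that the form's 4 weeks run from the last dose. The number of events affected cannot be estimated from the protocol.

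**What to change.** Reconcile 5.3.3.2, 5.3.3.8, the visit schedule with footnote J, and 8.1.4 so that there is one AE documentation period and one SAE reporting period.

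- For operated patients, run the SAE form and all-cause AE documentation at least to the end of the 90-day postoperative window that footnote J already uses. Collect at the 1-week, 1-month and 3-month (EOT) visits, where AEs are already marked.
- Do not shorten the documentation duty in 5.3.3.8 to achieve consistency.
- State the period to which the 24-hour report applies.
- State the periods for patients who are not operated on, for whom footnote J and 5.3.3.8 conflict in the same way.
- Reconcile the two EOT windows and the two drug safety visit windows.

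The change is a wording amendment that needs ethics approval and adds no visits. The real cost is workload: more SAE forms and, if the 24-hour report is extended, more expedited reports to authorities and ethics committees. That load may not be small, because prolonged hospitalization after cystectomy counts as an SAE under 8.1.3.

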9.1 Case Report Form

9.2 data management

The investigator should arrange for the retention of study documents until the end of the study.

In addition, investigators should follow specific local regulations/guidelines regarding the custody of patient records.

Unless otherwise stated in the investigator's agreement, it is recommended that the investigator preserve the study documentation for at least five years after study completion or discontinuation, in accordance with other criteria and/or local law.

X. Ethical requirements

This study was in compliance with the Provisions of Good Laboratory Practice (Good Laboratory Practice) and Administrative Measures for Investigator-sponsored Clinical Studies in Medical and Health Institutions (for Trial Implementation) and the Declaration of Helsinki. This study could be conducted only after the protocol was approved by the Ethics Committee of our hospital before the start of the trial. During the course of the study, if protocol revision is necessary, the revised protocol must be resubmitted to the Ethics Committee for review, and the investigator must wait for the consent of the Ethics Committee before implementing the new protocol.

An informed consent form must be signed by each enrolled patient. A copy of the informed consent form and contact information for the investigator and ethics committee must be provided to the requested patient *. The clinical data and personal information of the research subjects were collected by this research society for scientific research, which would involve the privacy rights of patients. Participants in the study and the data analysts signed a confidentiality agreement not to divulge the patient's personal information and disease-related information to any individual or institution not related to the study. The collected patient data are subject to unified management, so as to prevent personal privacy leakage.

References:

- [1] Nat Med. 2019 Nov; 25(11):1706-1714. doi: 10.1038/s41591-019-0628-7. Epub 2019 Nov 4.
